### 8.3.2 Secondary Endpoint Analyses

The VAS score for tooth sensitivity for the first 7 days during the tooth bleaching period will be analyzed using a Mixed Model with Repeated Measures (MMRM), with study product, DH diagnosis at screening (yes/no), days of bleaching and study product by days of bleaching interaction as fixed effects. The VAS score at screening will also be included as a covariate. Subject will be included as a repeated measure with compound symmetry covariance structure. Kenward Rogers degrees of freedom approach will be applied ([Kenward and Roger, 1997](#)). The overall (across all days) least square means (with SE and 95% confidence intervals [CI]) for each study product will be presented along with the difference (with SE and 95% CI).

A separate MMRM will be applied to evaluate the pairwise differences between products for each day. This will be identical to the above MMRM but subject will be included as a repeated measure with unstructured covariance matrix. In case of convergence issues, the Toeplitz, Autoregressive (1), Compound Symmetry covariance structures will be applied until convergence is attained (all heterogeneous versions first and then the same sequence of homogeneous versions). The least square means (with SE and 95% CI) for each study product will be presented along with the pairwise differences (with SE and 95% CI) between products for each day using the appropriate contrasts from the MMRM results.

As a further sensitivity analysis, the mean VAS score for tooth sensitivity over the tooth-bleaching period (Visit 2 [at home] to Visit 3) for a subject will be analyzed using an Analysis of Covariance (ANCOVA) model will be used with study product and DH diagnosis at screening (yes/no) as fixed effects and the VAS score at screening as a covariate. The least square means (with SE and 95% CI) for each study product will be presented along with the difference (with SE and 95% CI).

The LMS and the Bothersomeness scores during the tooth-bleaching period will be analyzed and presented in identical fashion to the VAS scores endpoint using the same MMRMs and ANCOVA (replacing the respective screening result as a covariate).

For the % tooth sensitivity-free days and the % days analgesics used to alleviate tooth sensitivity during the tooth bleaching period, a negative binomial model will be applied to the number of days with the event. Study product and DH diagnosis at screening (yes/no) will be fitted as fixed effects. An offset variable for the number of days the daily question related to tooth sensitivity (Yes/No) was completed during the tooth bleaching period will be included to adjust for missing days in estimating the rates. The back transformed rates for each study product group and ratios between rates will be presented along with 95% CIs.

Each analysis assessing tooth sensitivity during the tooth bleaching period will also be applied to the same tooth sensitivity endpoints during the post-tooth bleaching period.

The tooth sensitivity scores at Visit 2 (prior to bleaching) will not be included in the analyses as a covariate because it is expected that the randomized product group at Screening will have

Property of Haleon- Confidential

May not be used, divulged, published or otherwise disclosed without the consent of Haleon

a causal effect on this outcome. Low tooth sensitivity following tooth bleaching should not be adjusted in the analysis for low tooth sensitivity at Visit 2, as this could be lower in general for subjects randomized to test and reference dentifrice groups at Visit 1.

An ANCOVA model will be applied to analyze the change in the mean VITA Shade score from pre- to post-tooth bleaching (Visit 2-3) with study product as a fixed effect and the mean VITA-Shade color score at screening fitted as a covariate. The least square means (with SE and 95% CI) for each study product will be presented along with the difference (with SE and 95% CI).

The assumption of normality and homogeneity of variance in each parametric test applied (i.e. ANCOVA / MMRM) will be investigated. In case of violation of these assumptions, a suitable non-parametric test will be performed, and results will be provided to support the parametric results.

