#### 8.3.1 Primary Endpoint Analysis

The modified Intent-to-Treat (mITT) population will be used for the primary analyses.

The primary endpoints are:

- Daily VAS scores collected through the study
- Daily LMS scores collected through the study
- Daily Bothersomeness scores collected through the study
- Daily number and % of subjects with a tooth sensitivity-free day through the study
- Daily number and % of subjects with analgesic used to alleviate tooth sensitivity through the study

Property of Haleon- Confidential

May not be used, divulged, published or otherwise disclosed without the consent of Haleon

Each endpoint will be summarized descriptively at Screening and Visit 2 (pre-bleaching) as well as by each relative day within the tooth bleaching and post-tooth bleaching period.

Days within the tooth-bleaching period will be relative to the Visit 2 [at home] result (day 1) up to and including the result recorded on the day prior to Visit 3. Days within the post-tooth bleaching period will be relative to the result following Visit 3 (at home) (day 1) and include any results up to and including the day of Visit 4. The daily mean ( $\pm$  SE) profiles of VAS, LMS and Bothersomeness scores across the study (clearly denoting each period) will be plotted by study product group.

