**When completing this form please consider your experience over the last 24 hours**

Have your teeth been sensitive ? Y/N     **If NO do not complete any further questions.**

Please make a single vertical mark at the point on the line which represents the degree of overall tooth sensitivity (eg twinges, pain and other sensations in your teeth) that you have experienced **over the last 24 hours**

[figure not shown]
No Sensitivity	_____	Extreme Sensitivity
-------------------	-------	------------------------

For Site use only: \_\_\_\_\_ mm     \_\_\_\_\_ Initials

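### Sensitivity-free days cannot exceed the days answered, yet they are modelled as an unbounded negative binomial count; when such days are very common the 95% CIs are too wide and can pass 100%

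*Combined protocol and SAP*

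**What the plan says.** Section 8.3.2 analyses two percentage endpoints, sensitivity-free days and analgesic days, as counts: "a negative binomial model will be applied to the number of days with the event". Product and DH status are fixed effects. Exposure enters as follows: "An offset variable for the number of days the daily question related to tooth sensitivity (Yes/No) was completed". The output is described thus: "The back transformed rates for each study product group and ratios between rates will be presented along with 95% CIs". The same analysis "will also be applied to the same tooth sensitivity endpoints during the post-tooth bleaching period".

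The daily item in Section 9.10 is binary: "Have your teeth been sensitive ? Y/N". Section 8.3.1 sets the windows. Bleaching runs from the evening of Visit 2 to the day before Visit 3. The later period starts on the evening of Visit 3 and is to "include any results up to and including the day of Visit 4".

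On model checking, Section 8.3.2 says: "The assumption of normality and homogeneity of variance in each parametric test applied (i.e. ANCOVA / MMRM) will be investigated". No check, robust variance or bounded alternative is named for the count model, and there is no rule for a rate or limit above 100%.

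**The concern.** A subject who answers on 7 days can have at most 7 sensitivity-free days. The negative binomial with a log offset treats the count as open-ended, with a variance at or above its mean. As the sensitivity-free share nears 100%, the real variance shrinks towards zero while the model's variance cannot.

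Two things follow. Intervals for rates and rate ratios become wider than the data justify, and an interval for a percentage of days can extend past 100%. The loss is greatest where sensitivity-free days are most frequent, which is where a product that works would put them. Section 8.1 reports no formal sample size calculation and Section 2 sets no success criterion, so estimates and their intervals are what this study delivers.

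**Working it through.** **Plan's own figures.** The only sample-size arithmetic is in Section 4.1, and it reproduces: 90 × (1 − 0.02) = 88.2, about 88 evaluable. No figure is given for this model.

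**Inputs from the protocol.**
- About 30 per arm, allocated 1:1:1; 40–50% DH-positive (Sections 7.3 and 8.1).
- Bleaching period: Days 15 to 21, so m = 7 (6–8 with the visit window).
- Post-bleaching period: Days 22 to 36 inclusive, so m = 15 (13–17 with the visit window).

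**Assumed, because the protocol is silent.** p = 0.5–0.9 and r = 0.2–0.4, with some runs at r = 0 and 0.6.

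**Step 1: variance.** The true variance of the capped count is m·p·(1−p)·(1+(m−1)r). The model's minimum (Poisson) variance is m·p. Their ratio is (1−p)(1+(m−1)r). When this is below 1, the fit falls to the Poisson floor and the standard error is overstated by 1/√((1−p)(1+(m−1)r)).

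- m = 7, p = 0.8, r = 0.2: 0.2 × 2.2 = 0.44, factor 1.51.
- m = 7, p = 0.9, r = 0.2: 0.1 × 2.2 = 0.22, factor 2.13.
- m = 15, p = 0.9, r = 0.4: 0.1 × 6.6 = 0.66, factor 1.23.

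The break-even correlation, below which the standard error is overstated, is r0 = p/((1−p)(m−1)).

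**Step 2: simulation.** There were 2,000 beta-binomial trials per setting with 3 arms of 30, no product effect, 13/30 DH-positive per arm, an assumed DH odds ratio of 0.5 and no missing days. The planned model was fitted by maximum likelihood, as Poisson when the dispersion reached 0. The table shows the model SE divided by the true SD of the log rate ratio, over r = 0.2–0.4.

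| p | r0, 7 days | SE ratio, 7 days | r0, 15 days | SE ratio, 15 days |
|---|---|---|---|---|
| 0.5–0.6 | 0.17–0.25 | 1.00–1.09 | 0.07–0.11 | within 1.00–1.13 |
| 0.7 | 0.39 | 1.05–1.22 | 0.17 | within 1.00–1.13 |
| 0.8 | 0.67 | 1.22–1.52 | 0.29 | 1.02–1.15 |
| 0.9 | any r | 1.72–2.11 | 0.64 | 1.24–1.65 |

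Where r was below r0, simulation and formula agreed to within 0.04.

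Null rejection against a nominal 5%:
- 7 days: 0.3–1.6% at p = 0.8 and 0–0.3% at p = 0.9.
- 15 days: 2.2–4.6% at p = 0.8 and 0–1.0% at p = 0.9.

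**Step 3: limits above 100%.** At the floor, an arm's upper limit is p·exp(1.96/√(n·m·p)). With n = 30 it exceeds 1 once the observed rate passes about 86.5% (m = 7) or 90.8% (m = 15).

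Example with m = 7, p = 0.9, r = 0.2:
- Planned model: n·m·p = 189, SE(log rate) = 1/√189 = 0.0727, CI 78.0% to 103.8%.
- Clustered binomial on the logit scale: SE(p) = √(0.09 × 2.2/210) = 0.0307, SE(logit) = 0.0307/0.09 = 0.341, CI 82.2% to 94.6%.
- Rate ratio: the CI factor is exp(1.96 × √(2/189)) = 1.22, against exp(1.96 × √(2/189)/2.13) = 1.10 with the true variance.

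Share of simulated trials with at least one of the three products' upper limits above 100%:
- p = 0.8: 8–18% (7 days), 0.1–3.5% (15 days).
- p = 0.9: 99% (7 days), 71–77% (15 days).

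Product-level point estimates never passed 100%. A fitted DH-negative rate did so in at most 7% of trials.

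**Step 4: proposed model on the same data.** Quasi-binomial logistic regression gave null rejection of 3.8–5.4% and SE/true SD of 0.94–1.02 across all 30 settings (2 period lengths × 5 values of p × 3 values of r).

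**The case against.** The strongest reply is that the harm rests on values the protocol does not give, and that its own expectations point away from a high p during bleaching. Section 3 expects sensitivity to rise during bleaching and for 1–10 days after, and 40–50% of subjects must have confirmed DH. That stands, and it is why the size is stated conditionally. At p = 0.7, r = 0.3 over 7 days, the ratio CI factor is only about 1.26 against 1.23. Over 15 days at p = 0.7–0.8 the intervals are close to nominal.

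Stronger clustering also shrinks the effect. In a further simulation of 300 trials per setting, the 7-day SE ratio at r = 0.6 was 1.06 at p = 0.8, but still 1.55 at p = 0.9.

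No decision rests on these intervals, and the error is conservative. Both points are correct, and they limit the seriousness.

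Section 8.3 allows amendments and clarifications to be documented at blinded data review. That route is generic; it neither names a check of this model nor corrects it.

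Evening forms returned at Visit 4 may give 14 days rather than 15. With m = 14 and p = 0.9 the factors are 1/√(0.1 × 3.6) = 1.67 at r = 0.2 and 1/√(0.1 × 6.2) = 1.27 at r = 0.4, so nothing changes.

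Finally, a sandwich variance with the log link would keep the planned rate ratios; it gave 92–97% coverage in the 300-trial simulations. It repairs the width but does not keep limits below 100%.

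**Conclusion.** The concern holds. The mismatch between a capped yes/no count and an unbounded model is certain from the text. Its cost is conditional on p and r, which are assumptions here. For r = 0.2–0.4 it is small at p of about 0.5–0.6, and at 0.7–0.8 in the longer period. It is material from about p = 0.8 in the bleaching period and about p = 0.9 afterwards. There the standard errors are overstated by roughly 20% to 110%, and at p = 0.9 upper limits above 100% are usual.

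Type I error is not inflated; the loss is precision and readability on a secondary endpoint of an exploratory study. Rare analgesic days are little affected: at an assumed p = 0.05 and m = 7, r0 = 0.05/(0.95 × 6) = 0.009, so almost any clustering takes the variance above the floor. The change should be made, but the study's validity does not depend on it.

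**What to change.** In Section 8.3.2, replace the negative binomial model, in both periods, with an overdispersed binomial (quasi-binomial or beta-binomial) logistic model for event days out of days answered. Keep product and DH diagnosis as fixed effects. Missing days are handled by the denominator, which does the job intended for the offset. Report the adjusted percentage of days per product, with limits formed on the logit scale so that they stay within 0–100%, and product differences or odds ratios with 95% CIs. The same model can be used for analgesic days for consistency, although little is gained there.

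The cost is a change of SAP wording and a different standard procedure, made before database lock and unblinding. The one downside is that rate ratios give way to percentage-point differences or odds ratios.

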#### 6.3.1 Tooth Sensitivity Questionnaire

The tooth sensitivity questionnaire [including VAS and LMS] will be completed by the subject at the screening visit, at Visit 2 (prior to bleaching) to describe the overall tooth sensitivity experienced by the subject on that day. The questionnaire should then be dispensed to the subject to complete at home, in the evening, every day until they complete the study. Thus on the day of Visit 2 the subject should complete 2 questionnaires, one at site and one in the home. Thereafter the subject should complete 1 questionnaire per day at home.

Subjects will indicate whether they have felt tooth sensitivity during the previous 24 hours. Those who indicate they have not felt tooth sensitivity will not be required to complete the rest of the questionnaire. Subjects who indicate they did feel tooth sensitivity will complete the remainder of the questionnaire comprising the VAS, LMS and Bothersomeness numerical rating scale (NRS).

Subjects will rate their overall tooth sensitivity using a 100mm VAS with end anchors of 'No Sensitivity' to 'Extreme Sensitivity'.

The LMS apply psychophysical procedures (magnitude estimation and cross-modality magnitude matching) to condition specific descriptive words relevant to the subject's response ([Gracely et al., 1978](#)). The descriptive words are then aligned along a Visual Analogue Scale (VAS) at distances that reflect the psychological distances between words. These scales have been piloted and validated in a previously reported dentine hypersensitivity trials ([Heaton et al., 2013](#), [Mason et al., 2019](#)). The LMS will be used to rate the intensity, duration, tolerability

Property of Haleon- Confidential

May not be used, divulged, published or otherwise disclosed without the consent of Haleon

and descriptive quality of their tooth sensitivity using the four individual 100 millimetre (mm) LMS.

The study staff will measure the line segment marked-off in mm from bottom to top along the line (for LMS) and from left to right (for the VAS) and record this in the CRF.

The subject will also complete a NRS for bothersomeness for which the subject should circle an appropriate number on the scale.

All questionnaire data shall be recorded in the CRF upon return of completed questionnaire.

All questionnaire data shall be recorded in the CRF.

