### 8.3.3 Exploratory Analyses

Responses to the Post whitening questionnaire (separate questions and total score) will be analyzed between product groups using an independent t-test.

The change from screening in DHEQ total and domain scores at Visit 3 and Visit 4 will be analyzed between groups using separate ANCOVA models with study product as a fixed effect and the respective DHEQ total or domain score at screening as a covariate. The least square means (with SE and 95% CI) for each study product will be presented along with the difference (with SE and 95% CI).

All tooth-sensitivity endpoints will be summarized further, split by the whether the subject had confirmed DH at the screening assessment. Additional statistical testing may be performed using similar methods to those performed on the full mITT dataset.

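### The sensitivity-free-days model leaves out the pre-randomisation screening sensitivity answer: a low-priority improvement in precision at almost no cost

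*Combined protocol and SAP*

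**What the plan says.** Section 8.3.2 handles sensitivity-free days and analgesic days alike: "a negative binomial model will be applied to the number of days with the event", and "Study product and DH diagnosis at screening (yes/no) will be fitted as fixed effects". The only other term is "An offset variable for the number of days the daily question related to tooth sensitivity (Yes/No) was completed". The same analyses are then repeated for the post-bleaching period.

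The neighbouring models go further. The VAS MMRMs contain DH status, and in addition "The VAS score at screening will also be included as a covariate". The VAS ANCOVA takes product and DH status "as fixed effects and the VAS score at screening as a covariate". The LMS and bothersomeness models follow suit with their own screening results. The VITA shade ANCOVA uses the screening shade, and section 8.3.3 gives the DHEQ models "the respective DHEQ total or domain score at screening as a covariate".

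The screening information exists. Section 6.3.1 states that the tooth sensitivity questionnaire "will be completed by the subject at the screening visit". Section 3 places this before stratification and randomisation, and the form in section 9.10 opens with a Yes/No item on the last 24 hours that everyone answers. A No ends the form.

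Section 8.3.2 explains why Visit 2 scores are not covariates: subjects have by then used the randomised product for two weeks. It gives no reason for leaving out the screening answer.

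**The concern.** DH status is not the same thing as baseline symptoms. Under section 6.2.1 a subject counts as DH-positive only if a tooth to be bleached shows exposed dentine, MGI 0, mobility 0 and a Schiff score of at least 2, with no excluding feature. Someone who reports sensitivity but fails any one of these falls into the DH-negative stratum. Stratification therefore balances DH status but does not guarantee balance in symptoms, and the day-count model has no term to pick up what is left. The plan itself treats DH status as not enough for VAS, LMS and bothersomeness, since it adjusts those for both.

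This matters somewhat more here than elsewhere because the daily Yes/No item is answered whether or not the subject had symptoms, whereas the scale items are skipped after a No. Sensitivity-free days is thus the endpoint with the most complete daily record, in a study of about 30 subjects per arm.

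**Working it through.** **The plan's own figure.** Section 4.1 gives 90 randomised and about 88 evaluable at 2% dropout. 90 × 0.98 = 88.2 and 88 / 0.98 = 89.8, so the figure reproduces. The plan states no power, precision or correlation for the day counts (section 8.1: no formal sample size calculation).

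**Inputs from the documents.** 88 evaluable subjects, allocation 1:1:1, about 45% DH-positive (40 of 88), 7 bleaching days, 14 post-bleaching days, and a negative binomial model with product, DH status and an offset.

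**Assumptions not in the documents.** Screening Yes in 75% of DH-positive and 15% of DH-negative subjects; log-odds effect of DH on a sensitive day 0.7; log-odds effect of a screening Yes, beyond DH, of 0, 0.5, 1 or 2 (odds ratios 1, 1.6, 2.7 and 7.4); between-subject SD 1 or 2 on the logit scale for 7 days and 1.5 for 14 days; no product effect; no missing days; offset on the log scale.

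**Method.** Sensitive days were drawn as binomial out of 7 or 14, and sensitivity-free days were the remainder. The planned model was fitted with product + DH, then again with screening Yes/No added. Where no overdispersion was estimated the fit reduces to Poisson. There were 300 replicates per 7-day scenario and 80 per 14-day scenario.

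**Results, sensitivity-free days.** Percentages come from unrounded values; the SE is the median model SE of the log rate ratio.

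| Days | Effect | Between-subject SD | Model SE without → with | Change in model SE | Change in actual sampling SD |
|---|---|---|---|---|---|
| 7 | 0 | 1 | 0.124 → 0.125 | +0.5% | -0.2% |
| 7 | 0 | 2 | 0.154 → 0.154 | -0.2% | +0.2% |
| 7 | 0.5 | 1 | 0.129 → 0.130 | +0.4% | -1.8% |
| 7 | 0.5 | 2 | 0.166 → 0.165 | -0.3% | -0.4% |
| 7 | 1 | 1 | 0.134 → 0.134 | +0.2% | -5.7% |
| 7 | 1 | 2 | 0.181 → 0.176 | -2.3% | -1.7% |
| 7 | 2 | 1 | 0.153 → 0.144 | -5.6% | -17.1% |
| 7 | 2 | 2 | 0.211 → 0.194 | -8.1% | -6.7% |
| 14 | 0.5 | 1.5 | 0.091 → 0.090 | -0.7% | -0.9% |
| 14 | 1 | 1.5 | 0.103 → 0.099 | -3.3% | -4.2% |
| 14 | 2 | 1.5 | 0.135 → 0.118 | -13.0% | -16.0% |

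In some 7-day rows the reported SE hardly moves although the estimate does become more stable. A count capped at 7 can vary less than a Poisson count (first row: mean 4.44, variance 3.36), and the negative binomial SE cannot fall below the Poisson floor.

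**Chance imbalance.** With the same assumed rates, the within-DH variance of a screening Yes is 0.45 × 0.75 × 0.25 + 0.55 × 0.15 × 0.85 = 0.084 + 0.070 = 0.154. The SD of the difference between two arms of 30 is sqrt(2 × 0.154 / 30) = 0.10. A given pair of arms would differ by 10 percentage points or more in about one trial in three.

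**Analgesic days.** At a mean of about 0.5 days out of 7 (100 replicates per scenario), adding the screening Yes/No answer changed the model SE by 0.0% to -0.8%. Using instead a screening analgesic answer with 3% Yes (assumed) changed it by -1.4%, while the actual sampling SD rose by 1.3% and the added coefficient could not be estimated in about 16% of fits.

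**The case against.** The best defence is that this is a legitimate modelling choice. The VAS, LMS and bothersomeness models each adjust for the same scale at screening. A count of days has no like-for-like baseline, only one 24-hour answer taken two weeks before bleaching starts. DH status, which includes an air-stimulus response, is already in the model. Most of the sensitivity being counted is expected to come from bleaching, and nothing in the documents shows that one pre-bleaching day predicts it. All of that stands, and it is why the lower end of the gain is nil. It does not supply a reason for the omission, and the cost of adding the term is close to nothing.

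A reader might go further in four ways that the documents do not support:

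- **Bias.** Leaving out a prognostic covariate does not bias the randomised comparison on average. The study also has no formal success criterion (section 2).
- **A larger gain.** The linear formula 1 - sqrt(1 - R²) gives 5%, 11% and 16% for R² of 10%, 20% and 30%. Those R² values have no source in the documents, the range excludes no gain, and the formula does not describe a log-link model for a capped count.
- **Analgesic days.** The gain there is negligible. Daily users of medication that could affect sensitivity perception, analgesics among them, are excluded (section 4.3), and the analgesic item is asked only after a Yes, so the data may be sparse. A smaller model has a real advantage.
- **Screening VAS as well.** It is blank after a No, the plan has no rule for scoring it as 0, and alongside the Yes/No answer it would be a second, overlapping term.

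**Conclusion.** The point holds for sensitivity-free days only, as a matter of efficiency and consistency. The model omits a pre-randomisation response that the trial already collects, the comparable models adjust for theirs, and the stated reason about Visit 2 does not apply. Under the assumptions above, the reduction in the model SE runs from nil to about 8% over 7 days and up to about 13% over 14 days. The upper figures need a strong predictor (odds ratio about 7 beyond DH). If the answer predicts nothing, the model SE rises by at most about 0.5%. No conclusion of the study becomes invalid if the plan is left unchanged. Free improvement, low priority.

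**What to change.** In section 8.3.2, add the screening Yes/No sensitivity answer (last 24 hours) as one fixed effect, next to product and DH status, in the negative binomial model for sensitivity-free days, for both the bleaching and the post-bleaching period. Do not add the screening VAS, and leave the analgesic-days model unchanged. Record the change before unblinding; section 8.3 already allows clarifications to be documented in the blinded data review before database lock. The cost is one model parameter and one line of text, with no new data.
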